Title: Family Telemental Health Intervention for People with Dementia and their Caregivers

Protocol # 1567

Principle Investigator: [name]

Co-Investigators: [name]; [name]

Abstract:

The increase in prevalence of dementia over the last 50 years has resulted in a concomitant rise in the number of families facing the physical, emotional, and psychological stress associated with caregiving. Behavioral symptoms that occur in persons with dementia (PWD) lead to negative mental and physical health outcomes for caregivers and predict caregiver decisions to institutionalize PWD. Resources to Enhance Alzheimer's Caregiver Health - VA (REACH VA), has demonstrated its ability to improve caregiver burden, emotional and physical well-being, social support and management of behavioral symptoms. Although REACH VA represents one of the best available approaches to help caregivers, treatment non-response and modest treatment effects remain significant issues. A variety of factors may be associated with non-response to behavioral intervention — one particularly robust predictor of non-response is interpersonal skill.

The goal of this research project is the first step toward systematically identifying and addressing caregiver interpersonal challenges using telehealth technology. Observation via telehealth provides the physical and emotional distance for better identification of interpersonal behaviors that may be more difficult to achieve when in person in addition to providing the opportunity for recording interactions. This project involves three interrelated activities: (1) refinement and pilot testing of a video based observational coding manual (OCM) to evaluate interpersonal skills of family caregivers interacting with PWD (2) development of a treatment manual integrally linked to the OCM and (3) assessment of the feasibility of delivering the treatment.

Methods:

Participants: We anticipate that approximately a total of 20 caregivers will be recruited into the study. No participants will be excluded because of gender, race, health status, or marital status.

Although care recipients will have dementia, for those with mild to moderate dementia, evidence from prior studies demonstrate that such individuals often have decision-making capacity and are able to recognize the risk-benefit profiles of various research study scenarios. Care-recipients who refuse to participate in the study will not be approached again.

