(1) Refining and pilot testing the OCM: We will convene an Expert Advisory Panel (EAP) with expertise in interpersonal and family caregiving processes and family psychotherapy to provide feedback on the OCM. The OCM represents an adaptation of previously established and reliable coding manuals developed for assessing interaction patterns in couples, families, and dementia caregiver research. Using an iterative process of refinement based on EAP feedback, pilot coding of video from five initial dyads, and feedback from those dyads we will use coding schemes originally developed for research and adapt them for clinical use. We will then recruit 15 additional dyads and videotape their interactions. Five Psychology Trainees will be trained on the OCM. The PI and pairs of Psychology Trainees will independently code each video to assess validity (face, concurrent, convergent, discriminant, content, and criterion), reliability (alternate form, inter-rater, and internal consistency) and analyze qualitative data from semi-structured interviews of caregivers, care-recipients, and clinicians to assess acceptability and utility of the OCM.

(2) Development and pilot testing of the Family Intervention: As the OCM is being created, we will draft a treatment manual for a family intervention informed by established empirically supported interventions for couples and families. The treatment manual will specifically target the identified interpersonal skills deficits in the OCM. A draft of the Treatment Manual will be presented to the EAP, eliciting feedback for further refinement. We will pilot test the family intervention via telehealth with the dyads who received the OCM and assess feasibility of delivery, dyad benefit from dyad and therapist report, and descriptive analyses of changes in interpersonal conflict, caregiver depression, anxiety, and burden.

Study Visits and Measures:

Visits:

Dyads will be recruited in 2 waves.

In wave 1, 5 dyads (or more dyads until sufficient data is collected for the development of the intervention, estimated 5-10 dyads total) will be recruited and complete

1. First Contact,
2. *Assessment Session*
3. Recording Task
4. Feedback session, Caregiver Intervention is Offered

In wave 2, the remaining dyads will be recruited and complete

1. First Contact,
- 1a. *Assessment Session*,
2. Recording Task,
3. Family Therapy, and
- 3a. *Exit Measures*.

3b. *Therapist Exit Measures (Participants will not be present for this)*

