3. **Recording Task (1 hour, all waves):** We will use existing telehealth facilities and equipment to record dyads as they engage in the two OCM tasks. Research staff will bring participants to designated telehealth rooms and ensure the equipment is operating appropriately. They will then leave the room and a research staff will present the rationale and instruction for each task via the telehealth video monitors. The first task will be recorded for 10 minutes. After 10 minutes, research staff will provide instructions for a second 10-minute task via the telehealth video monitors. The second task will be recorded for 10 minutes.
 - a. **Task 1:** Dyads will collaboratively plan a hypothetical pleasant event. This task will allow clinicians to observe the caregiver's ability to involve the care-recipient in eliciting preferences, validating feelings and desires, demonstrating emotional engagement and connection, and providing appropriate structure and guidance around planning this hypothetical event.
 - b. **Task 2:** Dyads will work together to complete a puzzle. We will instruct caregivers to not solve the puzzle themselves but to assist care-recipients in the completion of the task. The task will allow clinicians to observe the caregiver's ability to reduce complex tasks into simple instructions, observe and modify the approach based on care-recipient reactions, regulate care-recipient frustration, and simultaneously attend to the care-recipient's feelings and the successful completion of the task.

2a. Feedback Session (30 minutes, Wave 1 only), Research staff will conduct semi-structured interviews separately with each member of the dyad to assess reactions to participating in the tasks, perceived benefit, ways to make the tasks more relevant, and willingness to participate in additional treatment following the tasks. Research staff will tailor the care-recipient interview to fit care-recipients' needs and verbal abilities.

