4. **The Dementia Caregiver Intervention (~4-6 weeks, Wave 1 only)** The intervention offers short-term therapy for caregivers of persons with dementia to assist in communication, problem-solving, and caregiver stress management. Some Dementia Caregiver Intervention intake measures overlap with the current study's intake battery, including the demographics forms, PHQ-9, GAD-7, and Zarit Burden Scale. Based on the First Contact eligibility results, the participant will be offered the opportunity to enroll and participate in both the current study and a separate caregiver intervention. Once consented, the participants will complete the additional caregiver intervention specified intake measures (the Adult Attachment Scale,

URICA Readiness for Mental Health Treatment, Dementia Severity Rating Scale, the Multidimensional Scale of Perceived Social Support, the Structured Clinical Interview for DSM-IV Axis II Personality Disorders, the Personality Assessment Inventory, and the Secure Base Script Assessment – Older Adult Version) in addition to the current study measures. This will only be offered to the first five participant dyads to enroll in the current study. Participants have the option to come in on a separate day to consent to and complete measures for the Dementia Caregiver Intervention.

5. Family Therapy (~12-16 weeks, Wave 2 only): Performed by Family Therapist [name]. Our development of the treatment manual will be informed by the specific interpersonal skills deficits identified in the process of refining the OCM. We anticipate that the treatment manual will be approximately 12-16 sessions and will include the following specific strategies, the implementation of which will be tailored by clinicians to the specific interpersonal deficits identified in the OCM: (1) psychoeducation on dementia, (2) communication and problem solving skills, (3) safety building skills, (4) relationship satisfaction enhancement skills, (5) “meaning making” (i.e. collaboratively identifying the personal significance of events), (6) identification of core patterns from dyad relationship history, (7) techniques to shift emotional responses, (8) techniques to increase emotional attunement, and (9) techniques to increase attunement to care-recipient needs

3a. Exit Measures (2 hours, Wave 2 only): The Exit Measures will be done in person with study staff. Tasks will include

- a. KCMS
- b. PHQ-9
- c. GAD-7
- d. Zarit

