6. Feedback Session Interview: We will conduct semi-structured interviews with the initial five dyads following the two interaction tasks of OCM V-2 for additional refinement in developing OCM V-3. Research staff will conduct semi-structured interviews separately with each member of the dyad to assess reactions to participating in the tasks, perceived benefit, ways to make the tasks more relevant, and willingness to participate in additional treatment following the tasks. Research staff will tailor the care-recipient interview to fit care-recipients' needs and verbal abilities. We will incorporate dyad feedback into OCM V-3.
7. Exit Measures Semi-Structured Interview: Similar to the Feedback Session Interview, yet modified for based on information gathered from that interview. This will be given to the 15 dyads in Wave 2.
8. Therapist Exit Measures: Research staff will conduct semi-structured interviews with Family Therapist to gather data on their experience providing the treatment and potential modifications to both the treatment and the OCM based on therapist experience providing the family intervention.

OCM Development:

OCM Versions: OCM Version-1 (V-1) is adapted from established and reliable coding manuals designed to assess interaction patterns in couples, families, and dementia caregiver research. We will create OCM V-2 based on EAP guidance and feedback. OCM V-3 will be created based on pilot testing on 5 dyads and dyad feedback. OCM V-4 will be developed based on a second round of EAP feedback. We will use OMC V-4 to train interventionists, who will pilot test it with 15 dyads for reliability, validity, and utility.

Expert Advisory Panel: We will use two rounds of feedback from an Expert Advisory Panel (EAP) with expertise in family caregiving processes and two rounds of pilot testing with dyads to refine and test the OCM. EAP members will not be exposed to PHI.

Expert Advisory Panel Members	Institution	Expertise
[name]	Penn State University, Dept. of Human Dev. and Family Studies	Co-Creator of Cognitive Behavioral Conjoint Therapy for PTSD and developer of observational coding protocol for family emotional involvement
[name]	University of California – Los Angeles, Semel Institute	Creator of Family Focused Therapy for Bipolar Disorder and expert in family observational coding
[name]	New York University, New York Center for Emotionally Focused Therapy	Expert in Emotion Focused Therapy for couples

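### Does promising alternate-form reliability for the coding manual, without naming a second form, require a change to the plan?

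*Combined protocol and SAP*

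**What the plan says.** Procedure, item (1), on refining and pilot testing the OCM, lists three kinds of reliability to be assessed from the coded videos: "reliability (alternate form, inter-rater, and internal consistency". This is the only mention of an alternate form in the document.

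OCM Development, under OCM Versions, describes four versions, each a revision of the one before. Only the last reaches the reliability sample: "We will use OMC V-4 to train interventionists, who will pilot test it with 15 dyads for reliability, validity, and utility". The Training section has two trainees code each of those videos with V-4, with the PI as criterion coder.

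The Recording Task entry gives one visit with two tasks in sequence: "After 10 minutes, research staff will provide instructions for a second 10-minute task via the telehealth video monitors". Task 1 is joint planning, meant to show the caregiver "validating feelings and desires, demonstrating emotional engagement and connection, and providing appropriate structure and guidance around planning this hypothetical event". Task 2 is a puzzle, meant to show the caregiver's ability to "reduce complex tasks into simple instructions, observe and modify the approach based on care-recipient reactions, regulate care-recipient frustration", and also attention to the care-recipient's feelings. The exit visit ("3a. Exit Measures (2 hours, Wave 2 only): The Exit Measures will be done in person with study staff") lists questionnaires and an interview, with no second recording.

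The OCM part of Data Analysis is headed as validity and covers six validity types. Agreement between trainees and PI appears there under criterion validity. Neither alternate-form reliability nor OCM internal consistency has an analysis of its own.

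**The concern.** Alternate-form reliability needs two versions of an instrument applied to the same subjects. Here there appears to be one instrument, one recording visit and no analysis, so one of three promised properties seems undeliverable.

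The obvious substitute, correlating Task 1 with Task 2, raises a second worry. The tasks target partly different skills, they are described as first and second with no mention of counterbalancing, and the same coders score both. The correlation could mix real differences in skill, task and order with measurement error, and shared coder impressions could push it up. If it were reported simply as reliability, readers could misjudge how dependable the OCM is. What is at stake is the psychometric description of the OCM, not any statement about the treatment.

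**Working it through.** The plan gives no figure for alternate-form reliability, so there is nothing to reproduce. The check asks what could serve as the second form, what the resulting number would mean, and what depends on it.

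**1. Candidates for a second form**
- *Another version of the manual.* V-2 is pilot tested on the first five dyads, whose videos then illustrate V-4 training. No video is scheduled for coding under two versions, so this is not available.
- *A second recording.* None is listed at exit, so this is not available.
- *The two tasks.* Same dyads, same visit, one manual, 10 minutes each. This is available, although the text never says it is what was meant.

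**2. What a between-task correlation would measure**

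Assume each task score has reliability 0.80, true scores correlate r_T across tasks, and coding errors correlate c. None of these values is in the documents. Then

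observed r = 0.8 × r_T + 0.2 × c.

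| c | r_T = 0.3 | r_T = 0.5 | r_T = 0.7 |
|---|---|---|---|
| 0 | 0.24 | 0.40 | 0.56 |
| 0.5 | 0.34 | 0.50 | 0.66 |
| 1 | 0.44 | 0.60 | 0.76 |

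Setting observed r to 0.80 gives the break-even r_T = (0.8 − 0.2c)/0.8 = 1 − 0.25c. This is 1 at c = 0, 0.875 at c = 0.5 and 0.75 at c = 1. With independent errors the coefficient therefore cannot exceed the reliability and serves as a lower bound. It overstates reliability only when the tasks tap nearly the same skill and coder errors are also shared. No cell of the table reaches 0.80.

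**3. Order**

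If going second shifts every dyad's Task 2 score by the same amount k, then corr(X1, X2 + k) = corr(X1, X2), and the ranks do not move either. Only order effects that differ between dyads matter. That the order is fixed is itself an inference from the task labels.

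**4. Precision**

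The 95% CI for a Pearson correlation is tanh(atanh(r) ± 1.96/√(n − 3)). The plan states 15 wave 2 dyads. Wave 1 may grow ("or more dyads until sufficient data is collected for the development of the intervention, estimated 5-10 dyads total") and the total is approximate ("approximately a total of 20 caregivers will be recruited into the study"), so a low case is 20 − 10 = 10.
- n = 15, half-width 1.96/√12 = 0.566 on the z scale: r = 0.5 gives −0.02 to 0.81; r = 0.8 gives 0.49 to 0.93.
- n = 10, half-width 1.96/√7 = 0.741: r = 0.5 gives −0.19 to 0.86; r = 0.8 gives 0.34 to 0.95.

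The interval is this wide whether the coefficient is called alternate-form reliability or cross-task consistency.

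**5. What depends on it**

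The concurrent, convergent and discriminant analyses use OCM V-4 summary scores. Criterion validity uses agreement with the PI. Face and content validity use interviews and panel ratings. The treatment summaries use retention, the questionnaires and within-group effect sizes. None takes an alternate-form coefficient as input.

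**The case for a change.** The strongest case for a change is that reliability is an explicit aim of the 15-dyad stage, and a plan should not list a property that its design does not identify how to measure. If the two tasks were intended, one sentence would say so, and calling the figure cross-task consistency would prevent over-reading. The cost is wording alone.

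The textual part stands: the term is undefined, and the plan also leaves the trainee-to-trainee coefficient and the OCM internal-consistency calculation unstated. The halo point stands too, because the same coders score both tasks and the direction of bias is not guaranteed.

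The step from there to a required change is weaker. Alternate-form coefficients count differences in content between forms as error by design, so partly different tasks make the figure conservative rather than meaningless. How parallel the tasks must be is something statisticians could dispute, particularly as both include feelings and guidance. The missing coefficients are ordinary detail: two trainees already code each video and the item scores will exist, so an analyst can choose a suitable intraclass correlation and internal-consistency measure without any change in design.

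**Conclusion.** The plan uses a term it does not define, and nothing more follows. Removing the term, or naming the two tasks as the forms, would leave every recording, every coded video and every analysis under Data Analysis as it is. An analyst would either report the Task 1 to Task 2 correlation with its interval, noting that it also reflects task differences, or report only inter-rater agreement and internal consistency.

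The size is one item of three in a list of reliability properties, in a pilot of about 20 dyads, with no treatment conclusion attached. This rests on two readings of the text: that the tasks are the only available pair of forms, and that no planned analysis uses the coefficient. The correlations in the table rest on assumed inputs and show only how such a figure behaves, not what this study would find.

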4. Discriminant Validity will be established by examining the correlation between the OCM V-4 summary score and variables anticipated to be unrelated or less related to interpersonal difficulties (e.g. HABC Monitor cognitive and functional subscales, education, SES, religion). We anticipate OCM V-4 scores to show no or small correlations with these variables. We will also compare the mean OCM V-4 summary scores of caregivers who experience significant caregiver burden or depression (PHQ-9>5 or Zarit Burden Scale >9) to those who do not report significant burden and depression to determine whether the

identified interpersonal variables differentiate caregivers who are experiencing significant distress from those who are not.

5. Criterion Validity will be established by examining inter-rater reliability of the trainee's coding with those of the PI as the Criterion Coder. We anticipate that the trainees will show good reliability with the Criterion Coder.
6. Content Validity will be established by calculating a content validity ratio to analyze the EAP's evaluation of each item in the OCM as "essential," "useful, but not essential," or "not necessary."

Dyad Perceived Feasibility and Utility of Treatment: Following treatment, research staff will assess caregivers with the KMCS, PHQ-9, GAD-7, Zarit burden scales and conduct semi-structured interviews with caregivers (and care-recipients, when possible) to assess reactions to the treatment, perceived benefit, feedback how to make the treatment more relevant, and willingness to refer others to the treatment. We will summarize retention rates and conduct descriptive analyses of the primary outcomes (mean with SD, median with IQR, boxplot, and frequency table) at baseline and post treatment. Within group effect sizes (Cohen's d) will be calculated. The constant comparative method of analysis will be used to analyze qualitative interview data.

Clinician Perceived Feasibility and Utility of Treatment: Research staff will conduct semi-structured interviews with family therapists to gather data on their experience providing the treatment and potential modifications to both the treatment and the OCM based on therapist experience providing the family intervention. Research staff will record and transcribe all interviews for qualitative analysis. The constant comparative method of analysis will be used to analyze qualitative interview data.

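### Does letting wave 1 grow to 10 dyads undermine the 15 dyads planned for wave 2?

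*Combined protocol and SAP*

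**What the plan says.** All references are to the combined protocol and SAP.

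- **Total.** Methods, Participants: "We anticipate that approximately a total of 20 caregivers will be recruited into the study".
- **Wave 1.** Study Visits and Measures, Visits: "In wave 1, 5 dyads (or more dyads until sufficient data is collected for the development of the intervention, estimated 5-10 dyads total".
- **Wave 2.** The same section gives no number: "In wave 2, the remaining dyads will be recruited and complete" a list of steps that includes Family Therapy and the exit measures.
- **Exit interview.** Measures, item 7: "This will be given to the 15 dyads in Wave 2".
- **Treatment data.** The visit descriptions restrict therapy and exit assessment to the second wave: "Family Therapy (~12-16 weeks, Wave 2 only") and "3a. Exit Measures (2 hours, Wave 2 only"). Under Procedure (2), the treated group is described with neither a wave nor a count: "We will pilot test the family intervention via telehealth with the dyads who received the OCM".
- **Analysis.** Data Analysis, Dyad Perceived Feasibility and Utility of Treatment: "We will summarize retention rates and conduct descriptive analyses of the primary outcomes" at baseline and after treatment, with within-group Cohen's d.

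Procedure (1), OCM Versions and Training all use the same fixed split: five dyads to develop the observational coding manual (OCM) and train coders, then 15 more whose videos are coded with version 4.

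**The concern.** A wave 1 of 5 to 10 and a wave 2 of 15 fit a total of 20 only at the bottom of the wave 1 range. Above five, either the 15 or the 20 has to move, and no section says which. Wave 2 is the only source of treatment retention, exit interviews and pre-post change, so these carry the abstract's aim of assessing whether the treatment can be delivered. A reader cannot tell whether 15 or as few as 10 dyads are meant to be treated.

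A sixth wave 1 dyad would also have no clear place in the plan. The visit description gives the feedback session to wave 1, while Measures item 6 names only the initial five dyads. The Dementia Caregiver Intervention is limited to the first five to enrol. Nothing says whether the recordings of later wave 1 dyads join the version 4 coding set.

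**Working it through.** **Inputs from the plan.** Total about 20 (Participants). Wave 1 of 5, or an estimated 5 to 10 (Visits). Wave 2 of 15 (Measures, item 7). Each dyad has one caregiver.

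**Reproducing the plan's figure.** Wave 2 = total - wave 1 = 20 - 5 = 15. The base plan is consistent.

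**Using the extension.** Either the total is held (wave 2 = 20 - wave 1) or wave 2 is held (total = wave 1 + 15).

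| Wave 1 | Wave 2 if total is 20 | Change from 15 | Total if wave 2 is 15 |
|---|---|---|---|
| 5 | 15 | 0% | 20 |
| 6 | 14 | -7% | 21 |
| 7 | 13 | -13% | 22 |
| 8 | 12 | -20% | 23 |
| 9 | 11 | -27% | 24 |
| 10 | 10 | -33% | 25 |

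The plan leaves both columns open. The total is approximate and 15 additional dyads are to be recruited, which favours holding 15. Describing wave 2 as the remainder favours holding 20.

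**Coding of version 4.** At a total of 20, the dyads outside the initial five number 20 - 5 = 15 whatever the size of wave 1. The recording task and the baseline battery cover both waves, so the material for 15 coded dyads exists in every case. No shortfall in the reliability or validity data is shown.

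**Precision of the treatment data.** The plan gives no effect size, retention rate or confidence level. I assumed all three, scaled d by the SD of the change, and took every wave 2 dyad as completing. The interval for d inverts the noncentral t distribution with t = d√n and n - 1 degrees of freedom. At d = 0.5 and 95%:

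| n | Interval for d | Width | Ratio to n = 15 |
|---|---|---|---|
| 15 | -0.05 to 1.03 | 1.077 | 1.00 |
| 13 | -0.09 to 1.07 | 1.157 | 1.07 |
| 12 | -0.11 to 1.09 | 1.205 | 1.12 |
| 10 | -0.17 to 1.15 | 1.321 | 1.23 |

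At n = 10 the ratio is 1.253/1.023 = 1.22 for d = 0.2 and 1.438/1.170 = 1.23 for d = 0.8, so it hardly depends on the assumed effect.

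For retention of 80%, the exact (Clopper-Pearson) 95% interval is 52% to 96% for 12 of 15, and 44% to 97% for 8 of 10.

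**Reading the result.** At d = 0.5 the interval runs from below zero to above one at every size in the table. Losing up to five treated dyads makes an imprecise estimate somewhat less precise. It introduces no bias and overturns no planned decision, because none is tied to these figures.

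**The case for a change.** The strongest case for a change is that five is the bottom of the sponsor's own estimate, so the figures agree at only one end of a range the plan itself gives. The looseness of an approximate 20 helps for a wave 1 of six or seven. At 10, it would have to absorb either a third fewer treated dyads (5/15 = 33%) or a quarter more dyads in total (5/20 = 25%). Extra wave 1 dyads cannot refill the treated group, because family therapy is confined to wave 2. The repair would be a sentence or two.

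The arithmetic stands, and so does the observation that no section says which number gives way. Three things limit its force.

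- The mismatch is conditional. It does not exist unless the extension is used.
- Neither repair improves a result. Restating wave 2 as 10 to 15, or the total as 20 to 25, documents the same study. Fixing wave 1 at five would remove the freedom to keep recruiting until the intervention can be developed, which is a reasonable thing to want at this stage.
- The loose ends around dyads six to ten are smaller than they look. OCM Versions and Training already separate the five development dyads from the 15 coded ones. First Contact allows wave 1 dyads to be screened for caregiver interventions other than the Dementia Caregiver Intervention, so the first-five limit need not conflict with it. What remains open is who receives the feedback interview and whether later wave 1 videos are coded. Both can be settled and reported as the study runs.

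**Conclusion.** The concern is accurate as a description and does not call for a change. The planned count for wave 2 is 15 if wave 1 stops at five. If wave 1 is extended, either wave 2 falls to between 10 and 14 at a total of 20, or the total rises to between 21 and 25 with wave 2 kept at 15. In the worst case the interval for the pre-post effect is about 23% wider than with 15 dyads, under the assumptions stated with the calculation.

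This is a gap that analysts fill sensibly. Retention would be reported over the dyads who entered treatment, and Cohen's d over those with baseline and exit measures, with the counts shown. That gives sound descriptive results whichever number moves. The conclusion rests on the treatment outcomes staying descriptive. Had the plan attached a test, a precision target or a go/no-go threshold to them, the treated number would need to be fixed.
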